## 5.4 Screen failures

Screen failures are defined as study participants who consent to participate in the clinical study but are not subsequently randomly assigned to study treatment. A minimal set of screen failure information is required to ensure transparent reporting of screen failure study participants to meet the Consolidated Standards of Reporting Trials publishing requirements and to respond to queries from regulatory authorities. Minimal information includes demography, screen failure details, eligibility criteria, and any SAE.

Individuals who do not meet the criteria for participation in this study (screen failures) may be rescreened (Section 5.5).

Tests that result in ALT, AST, or ALP up to 25% above the exclusion limit may be repeated once for confirmation. This includes rescreening.

## 5.5 Rescreening

Per investigator discretion, study participants may be rescreened once under conditions such as the following:

- Study participant falls outside the Screening Period
- If a study participant does not meet the inclusion criteria at Screening or on Day -1 due to an out-of-range laboratory result or a minor illness, he/she can be rescreened once at the discretion of the Investigator. Provided all inclusion criteria are met at the second screening, the study participant can be included.

Study participants may be included if the repeat values for the laboratory screening criteria are within normal ranges and/or if repeat values show normalization of the out-of-range safety laboratory values, and/or after the study participant makes a complete recovery from the mild or moderate illness and if all other screening criteria are met.

Rescreened study participants are assigned a new study participant number from the number assigned at the initial screening.

## 6 STUDY TREATMENTS/INVESTIGATIONAL DEVICE

In this study, the term IMP refers to the bimekizumab drug product. The term device presentation refers to 2 different injection device presentations (bimekizumab-AI-1mL and bimekizumab-AI-2mL) that are comprised of drug product (IMP) associated with a functional secondary packaging.

Bimekizumab will be supplied by UCB Clinical Trial Supply Operations or designee as a clear to opalescent, colorless to slightly yellow-brown, sterile, preservative-free solution, suitable for injection by sc administration, in either a 1mL prefilled syringe (PFS) or a 2mL PFS at a nominal concentration of 160mg/mL (55mM sodium acetate, 220mM glycine, 0.04% polysorbate 80 at pH 5.0) for sc administration.

## 6.1 Treatments administered

The treatments to be administered are presented in [Table 6-1](#).

**Table 6-1: UP0119 treatments administered**

Study Treatment Name	Bimekizumab-AI-2mL	Bimekizumab-AI-1mL
Drug product:	2mL PFS	1mL PFS
All treatments: a nominal formulation of 160mg/mL in 55mM sodium acetate, 220mM glycine and 0.04% (w/v) polysorbate 80 at pH5.0		
Total dose:	320mg	320mg
Duration of treatment:	Single dose	Single dose
Number of injections:	1x320mg	2x160mg
Route of administration:	sc	sc
Site of injection:	Thigh (left or right)	Thigh (1 in left and 1 in right)
Device:	2mL AI	1mL AI

AI=auto-injector; PFS=prefilled syringe; sc=subcutaneous

The IMP will be given in the thigh without massage. For bimekizumab-AI-1mL, the injection should continue until a second click is heard (to give an injection time of up to 15 seconds). For the administration of the 2x1mL, each sc injection should be given in a separate thigh (but at the same relative site of the thigh) with a maximum time of 60 seconds between injections. The exact timing of the injection(s) should be recorded in the electronic Case Report Form (eCRF). For bimekizumab-AI-2mL, the injection will take approximately up to 20 seconds until the second click is heard. After the second click, continue to hold down the AI for an additional 5 seconds to ensure the full dose is delivered.

Further details on how to proceed in the event of malfunction of any of the devices will be provided in the IMP handling manual.

### 6.1.1 Medical devices

All medical device presentation deficiencies, including malfunction use error, and inadequate labelling, shall be documented and reported by the Investigator throughout the study (see [Section 8.3.7](#)) and appropriately managed by the Sponsor.

#### 6.1.1.1 Bimekizumab-AI-1mL

The bimekizumab-AI-1mL is a single-use AI with a passive needle-safety mechanism. The bimekizumab-AI-1mL consists of a 1mL glass PFS containing bimekizumab drug product within a customized Ypsomed Ypsomate device. This device presentation was approved in the EU on 20 Aug 2021.

**Figure 6-1: Bimekizumab-AI-1mL**

AI=auto-injector

#### **6.1.1.2 Bimekizumab-AI-2mL**

The bimekizumab-AI-2mL is a single-use AI with a passive needle-safety mechanism. The bimekizumab-AI-2mL consists of a 2.25mL glass PFS containing bimekizumab drug product within an Ypsomed Ypsomite device.

**Figure 6-2: Bimekizumab-AI-2mL**

AI=auto-injector

### **6.2 Preparation, handling, storage, and accountability requirements**

The Investigator or designee must confirm appropriate temperature conditions have been maintained during transit for all study treatment received and any discrepancies are reported and resolved before use of the study treatment.

Only study participants enrolled in the study may receive study treatment and only authorized site staff may supply or administer study treatment. All study treatments must be stored in a secure, environmentally controlled, and monitored (manual or automated) area in accordance with the labeled storage conditions with access limited to the Investigator and authorized site staff.

The Investigator, institution, or the head of the medical institution (where applicable) is responsible for study treatment accountability, reconciliation, and record maintenance (ie, receipt, reconciliation, and final disposition records).

In case an out-of-range temperature is noted, it must be immediately reported as per instructions contained in the IMP Handling Manual.

Appropriate accountability forms that reflect the receipt and use of the IMP and the investigational device presentations including IMP will be supplied to the investigational site. Details of any loss of the IMP and/or injection investigational device presentations due to breakage or wastage, non-use, destruction at the study site, or return to the Sponsor or designee must also be recorded on these forms. All supplies and pharmacy documentation must be made available throughout the study for UCB (or designee) to review.

The Investigator (or designee) is responsible for retaining all used, unused, and partially used IMP and investigational device presentations until returned or destroyed. The Investigator may assign some of the Investigator's duties for drug accountability at the study site to an appropriate pharmacist/designee.

The device presentations should be stored with a proper study participant identification number until the study has been completed. UCB will then instruct the Investigator to destroy them. Used device presentations can be stored at room temperature, preferably placed in the original packaging. Further details are provided in the IMP Handling Manual.

The IMP and investigational device presentations intended for the study cannot be used for any other purpose than that described in this protocol.

### **6.2.1        Retention samples**

As UP0119 is a BE study, retention samples are required to be kept at sites per FDA requirement. All information related to storage and quantity needed on site will be provided in the IMP Handling Manual.

### **6.3           Measures to minimize bias: randomization and blinding**

This is an open-label study.

A PAREXEL Biostatistician (or designee) will write the randomization plan, program and will provide a dummy output of the randomization lists for review and approval in order to ensure compliance to study requirements.

Study participant treatment assignment will be random throughout the study. Study participants will be randomized in a 1:1 ratio to each treatment group as described in Section [4.1](#).

Copies of each site's randomization list will be sent to the respective site before the start of the study to the following recipients:

- ClinBase™ setup designer
- Sponsor Drug Safety staff for SAE reporting
- Bioanalytical staff
- Site pharmacist and Pharmaceutical Services staff (for dispensing IMP)

Pharmacokinetic concentration data will not be available to the study team until after the last scheduled procedure for the last study participant in the study, so the decision to replace participants who dropped out or are missing PK visits can be made in an unbiased manner.

At the Screening Visit, each study participant will be assigned a unique 5-digit number from a range of numbers supplied by UCB. Once the Investigator determines that the study participant is eligible for the study, the study participant will be paired to another eligible study participant, matching by gender and bodyweight ( $\leq 10\text{kg}$  difference between the 2 participants) and manually assigned to the next 2 available randomization numbers by the Investigator or designee prior to dosing on Day 1. Ideally, the participant's body weight at admission (Day -1) should be used for pairing. Allocating in pairs will improve the precision of the comparison between treatments. Each specific randomization number will identify the pair a study participant belongs to and is tied to the treatment allocation on the randomization schedule, which can then be dispensed by the site pharmacist. This randomization number will also be recorded in the eCRF (ie, ClinBase; see Section 10.1.6).

Participants who withdraw from the study may be replaced at the discretion of the Investigator and Sponsor. Any replacement must match the gender and weight ( $\leq 10\text{kg}$  difference between the 2 participants) of the remaining participant being replaced and receive the same treatment as the participant being withdrawn from treatment.

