## 5.5 Immunogenicity Analyses

### 5.5.1 Anti-drug antibodies

Antidrug antibodies will be measured using a 3-tiered assay approach: screening assay, confirmatory assay and titration assay.

A screening cut point will be determined by the bioanalytical laboratory that will be used to determine the status of ADAb as “Positive Screen” (PS) or “Negative Screen” (NS). For samples presenting ADAb levels as PS, further confirmatory assay will be performed, and the result of which will be reported as either “Positive Immunodepletion” (PI) or “Negative Immunodepletion” (NI). Samples that are confirmed as positive (reported as PI) will be titrated, and the titer (reciprocal dilution factor including minimum required dilution [MRD]: 100) will be reported.

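### The randomization list goes to bioanalytical staff before the study starts, with no stated purpose and no statement that the assays are run without treatment codes

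*Protocol*

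**What the plan says.** Protocol 6.3, the section on measures to minimize bias, opens with "This is an open-label study". It then says: "Copies of each site's randomization list will be sent to the respective site before the start of the study to the following recipients". Four groups are named: the ClinBase setup designer, sponsor drug safety, bioanalytical staff, and the site pharmacist with pharmaceutical services. Two have a purpose attached: "Sponsor Drug Safety staff for SAE reporting", and the pharmacy group for dispensing. "Bioanalytical staff" stands alone, as does the ClinBase designer.

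The same section says that each randomization number identifies the pair and is tied to the treatment. It also withholds concentration data from the study team until the last participant's last procedure, "so the decision to replace participants who dropped out or are missing PK visits can be made in an unbiased manner".

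Protocol 8.6 derives all PK parameters, including the three primary ones, from the plasma concentrations. SAP 5.5.1 gives the laboratory a role in immunogenicity too: "A screening cut point will be determined by the bioanalytical laboratory". Protocol Table 6-1 gives the dose as "Total dose: 320mg 320mg" for the two arms.

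**The concern.** In an open-label device trial the participant and the site staff necessarily see which injector is used. The assay analyst does not have to. The usual reasons for giving a laboratory the allocation are to skip placebo samples, or to use a different analyte or method by arm. Neither appears in these documents, since every dosed participant receives the same drug at the same dose.

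Bioequivalence is decided on AUC, AUC(0-t) and Cmax alone (Protocol 9.4.1, SAP 5.4.2.1), and all three come from the laboratory's numbers. Antibody status also defines the population of one sensitivity analysis (SAP 5.4.2.3, item 3). If a sample is repeated, a run rejected or one of two results chosen by someone who could look up the arm, the sponsor cannot point to the plan to show that the choice was made blind. That is an avoidable weakness in a bioequivalence claim.

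**Working it through.** **1. The texts side by side**

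- Who receives the allocation: bioanalytical staff, before the study starts, no purpose stated (Protocol 6.3).
- What links a result to an arm: the randomization number is tied to treatment (Protocol 6.3), and data forwarded to the sponsor or its designee carry that number (Protocol 10.1.4). Participants also have a separate 5-digit number (Protocol 6.3). Which identifier is on the tubes is not stated.
- What the laboratory produces: the concentrations (Protocol 8.6, SAP 5.4.1.1) and the antibody cut point (SAP 5.5.1).
- What protects the assay: nothing stated. Protocol 8.6 and 8.10 and SAP 5.4.1 and 5.5.1 do not mention coded samples, blinded assay or a date before which the list stays closed.
- What the existing safeguard covers: it keeps concentrations from the study team. It does not keep allocation from the analysts.

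It follows that allocation is available to the analysts and no blinding is stated. It does not follow that they use it.

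**2. The plan's own figure**

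Protocol 9.9 gives 54 per group for 80% power at a ratio of 1.08 (or 0.93), CV 32%, limits 0.80 to 1.25. Exact two one-sided tests power for an unpaired parallel design, with log-scale SD = sqrt(ln(1 + 0.32²)) and 2n − 2 degrees of freedom:

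- ratio 0.93: power 80.0% at 54 per group, so 54 is reproduced;
- ratio 1.08: power 78.0% at 54 per group, and 58 are needed for 80%.

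With 10% loss, 54/0.9 = 60, as stated. The present point does not rest on these figures.

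**3. Context: the interval at the planning values**

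- Variance: ln(1 + 0.32²) = 0.0975.
- SE of the log ratio: sqrt(2 × 0.0975/54) = 0.0601.
- t(0.95, 106) = 1.659, so the half-width is 0.0997.
- 90% CI: exp(ln 1.08 ± 0.0997) = 0.978 to 1.193.
- Room to the upper limit: 1.25/1.193 = 1.048.

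**4. Context: the ratios seen for this device in UP0068**

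Appendix 11 gives the 2mL autoinjector a ratio of 1.150 with CV 28.6% for AUC, and 1.143 with CV 24.7% for Cmax. The same formula with 54 per group gives:

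- AUC: variance 0.0786, SE 0.0540, upper limit exp(0.1398 + 0.0895) = 1.258;
- Cmax: variance 0.0592, SE 0.0468, upper limit exp(0.1337 + 0.0777) = 1.235.

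With 60 per group the upper limits are 1.252 and 1.230.

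Steps 3 and 4 are unpaired, whereas the planned ANOVA includes pair. They show how close the interval may lie to the limit. They are not an estimate of laboratory bias.

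**The case against.** The best reply has four parts.

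- **The study is declared open-label and nowhere promises a blinded assay**, so no commitment is broken. This is true, but open-label status explains why the site knows the device, not why the analyst should. Section 6.3 itself adds a safeguard to an open-label study.
- **A reader might infer that the primary endpoint is assayed with treatment known.** The documents do not support that. They show that the list is sent, not that it is consulted. Sample handling is left to sponsor instructions and a laboratory manual, and re-assay rules are not described. Samples may already be coded and re-assay rules fixed in advance. This part stands and limits the claim.
- **The endpoint is a measured concentration, not a rating.** Bias could enter only through judgement calls, and nothing shows that occasional repeats could shift a whole arm's geometric mean by the 4.8% in step 3. This also stands.
- **A reader might combine the UP0068 ratios with the 32% planning CV**, obtain an upper limit of about 1.27 for AUC (1.271 at 54 per group), and conclude that tiny shifts decide the result. Appendix 11 gives this device's own, lower CVs, with which Cmax stays inside 1.25. For AUC, where the limit is already passed, only a shift lowering test relative to reference could turn failure into success.

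What remains is that the plan hands over the list without a reason, and neither document restricts its use.

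**Conclusion.** The point holds in a limited form. Treatment allocation is available, from before the first dose, to the staff who generate the data for all three primary endpoints. No purpose and no assay blinding are stated, and the equal active dose in both arms leaves no evident operational need for it. The size of any resulting bias cannot be derived from the documents and may be nil. The interval of about 0.98 to 1.19 at the planning values, and the recomputed UP0068 upper limits of about 1.26 (AUC) and 1.24 (Cmax) at 54 per group, are background only.

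The conclusion rests on what the two documents say. A laboratory manual or bioanalytical plan that requires blinded assay would remove most of the practical concern, but Section 6.3 would then still need to be brought into line with it.

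**What to change.** - In Protocol 6.3, delete the bioanalytical staff from the pre-study recipients of the randomization list.
- Add one sentence: bimekizumab concentration and antibody assays, including decisions on re-assay and on the reportable value, are made without treatment codes until the final bioanalytical data have been transferred.
- If the laboratory does need the list, state the reason and release it only after that transfer.

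The cost is one deleted entry, one added sentence and a matching note in the laboratory manual. No participant procedure, sample or analysis changes. The laboratory should confirm that its workflow does not depend on the list; nothing in the documents suggests that it does.

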#### **6.4 Treatment compliance**

All IMP will be administered by the Investigator or his/her appropriately trained designee.

#### **6.5 Concomitant medication(s)/treatment(s)**

##### **6.5.1 Permitted concomitant treatments (medications and therapies)**

The following concomitant medications are permitted during the study:

- Acetaminophen/paracetamol (maximum 2g/day)
- Oral contraceptives
- Hormonal postmenopausal treatment
- Herbal remedy or food supplements (eg, vitamins) within the recommended daily dose limits
- Short-term intake of over-the-counter/non-prescription drugs is allowed if judged by the Investigator to have no potential for drug-drug interactions with the IMP

Non-live vaccines (eg, inactivated influenza and pneumococcal vaccines or non-live COVID vaccines) are allowed up to 2 weeks prior to randomization and 2 weeks after dosing, at

minimum. Investigators can contact the UCB Study Physician or medically qualified designee/ equivalent for further guidance.

### **6.5.2 Prohibited concomitant treatments (medications and therapies)**

With the exception of those medications listed in Section 6.5.1 and medications necessary for the treatment of treatment-emergent adverse events (TEAEs) per Investigator discretion, no prescription or nonprescription medicines are allowed within 14 days (3 months for biologic agents) or 5 half-lives of the respective medication (whichever is longer), prior to randomization and until the SFU Visit (Day 140).

### **6.6 Dose modification**

Not applicable.

### **6.7 Treatment after the end of the study**

Not applicable.

## **7 DISCONTINUATION OF STUDY MEDICATION AND PARTICIPANT DISCONTINUATION/WITHDRAWAL**

### **7.1 Discontinuation of IMP**

Not applicable; eligible study participants are randomized to receive a single-dose administration of bimekizumab 320mg in UP0119.

#### **7.1.1 Criteria for study hold due to adverse events**

During the study, planned dosing and procedures must be discontinued or suspended for all remaining study participants who are yet to be dosed in the study and appropriate follow-up procedures established for (but not limited to) any of the following reasons:

- A pattern of adverse events (AEs), considered as related to the study drug, occurs that in the opinion of the Investigator and/or Sponsor Study Physician contraindicates the further dosing of additional study participants.
- If the Sponsor or its designee judges it necessary for medical, safety, regulatory, or any other reasons consistent with applicable laws, regulations, and Good Clinical Practice (GCP).

Where it is possible to do so without threatening the safety of study participants, such discontinuation/suspension should be discussed with the UCB Study Physician prior to its implementation.

Study and site closure information is provided in Section 10.1.8.

#### **7.2 Study participant withdrawal from the study**

Study participants are free to withdraw from the study at any time, without prejudice to their continued care and without having to provide any reason.

A study participant may withdraw from the study at any time at his/her own request, or may be withdrawn at any time at the discretion of the Investigator for safety, behavioral, compliance, or administrative reasons.

If the study participant withdraws consent for disclosure of future information, the Sponsor may retain and continue to use any data collected before such a withdrawal of consent.

If a study participant withdraws from the study, he/she may request destruction of any samples taken and not tested, and the Investigator must document this in the site study records.

Upon study discontinuation, an Early Withdrawal Visit will be conducted at the time of withdrawal and the same assessments planned for the SFU Visit per the Schedule of activities (Section 1.3) will be performed.

Study participants should be discontinued from the study if any of the following events occur:

1. Study participant develops an illness that would interfere with his/her continued participation as per the Investigator's judgment.
2. Study participant is noncompliant with the study procedures in the opinion of the Investigator.
3. Study participant takes prohibited concomitant medications as defined in this protocol.
4. Study participant withdraws his/her consent.
5. There is confirmation of a pregnancy during the study, as evidenced by a positive pregnancy test. Study participants should attend the SFU Visit following withdrawal.
6. The Sponsor or a regulatory agency requests withdrawal of the study participant.
7. Participation in any other study during the duration of this study.

Study participants must be withdrawn by the Investigator based on discussion with the Sponsor under the following circumstances:

- Any confirmed COVID-19 case that warrants discontinuation in the judgment of the Investigator or Sponsor to protect the safety of the study participant, other participants, or study site staff.

Investigators should contact the Medical Monitor, whenever possible, to discuss the withdrawal of a study participant in advance. Study participants will be encouraged to return for an SFU Visit following premature discontinuation from the study.

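### After the single dose, the discontinuation rule for prohibited medication in Protocol 7.2 can only cut short scheduled PK, antibody and safety observation

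*Protocol*

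**What the plan says.** Protocol 7.2 opens its list with "Study participants should be discontinued from the study if any of the following events occur", and item 3 reads "Study participant takes prohibited concomitant medications as defined in this protocol". The action is discontinuation from the study. For discontinuation of the study drug, Section 7.1 says: "Not applicable; eligible study participants are randomized to receive a single-dose administration of bimekizumab 320mg in UP0119".

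Protocol 6.5.2 sets the scope: "no prescription or nonprescription medicines are allowed within 14 days (3 months for biologic agents) or 5 half-lives of the respective medication". The ban starts before randomization and lasts until the Day 140 visit. It exempts the Section 6.5.1 list and "medications necessary for the treatment of treatment-emergent adverse events (TEAEs) per Investigator discretion".

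On discontinuation, 7.2 requires an Early Withdrawal Visit with the Safety Follow-Up assessments; the Schedule of activities includes a PK and an antibody sample there. A later Safety Follow-Up Visit is encouraged. Protocol 8.3.1 collects SAEs for 30 days after each participant's end of study. Protocol 6.3 allows, at discretion, a replacement matched on gender and weight who receives the same treatment.

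SAP 5.4.2.1 fits pair and treatment as fixed effects to log AUC, AUC(0-t) and Cmax, and allows a participant to count for some parameters and not others. SAP 5.4.1.2 leaves the PK parameters of early withdrawals to the PK scientist's judgment. Sensitivity analysis 6 in SAP 5.4.2.3 adds back excluded parameters that are available.

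**The concern.** In a multiple-dose trial, a rule of this kind can at least stop further exposure. Here nothing remains to be stopped after Day 1, so its only effect is on data. AUC and AUC(0-t) depend on serial samples to Day 140, and all three primary parameters must meet 0.80 to 1.25 for bioequivalence to be concluded. A participant who leaves early gives either no usable AUC or a truncated one. In the fixed-pair model a missing value also silences the matched partner, who was dosed and sampled in full. The loss arises after randomization and could have been avoided, since the remaining visits were already scheduled.

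**Working it through.** **1. The plan's own figure.** Inputs (Protocol 9.9): CV 32%, GMR 1.08 or 0.93, limits 0.80 and 1.25, 90% CI. The log-scale SD is sqrt(ln(1 + 0.32²)) = 0.312. Two one-sided t-tests with 54 per group give 80.0% power at GMR 0.93 and 78.0% at 1.08, so the stated 54 reproduces at 0.93. 54/0.9 = 60 reproduces the enrolment figure. Nothing in this point changes either number.

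**2. How much of AUC is observed by a given day.** Half-life 28 days (Protocol 4.2), so ke = ln 2/28 = 0.0248 per day. The documents give no absorption rate; ka = 0.2 to 0.5 per day is an assumption. For a one-compartment subcutaneous profile the fraction of total AUC observed by time t is

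1 − [ka·exp(−ke·t) − ke·exp(−ka·t)]/(ka − ke)

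Dosing is on Day 1, so Day 28 is 27 elapsed days; the ranges cover 27 and 28 days, and likewise for later visits.

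| Last sample | AUC observed | Extrapolated |
|---|---|---|
| Day 28 | 42-47% | 53-58% |
| Day 56 | 71-74% | 26-29% |
| Day 84 | 85-87% | 13-15% |
| Day 112 | about 93% | about 7% |
| Day 140 | 96-97% | 3-4% |

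The damage is therefore concentrated in early cases. Up to Day 56, extrapolation exceeds the 20% at which SAP Table 5-3 flags AUC. That table also asks for a terminal interval of at least two half-lives, 2 × 28 = 56 days, which a profile ending at Day 28 cannot contain if the estimated half-life is near 28 days.

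**3. What a truncated AUC(0-t) does if it is kept.** For a last sample at Day 28, its ratio to the same participant's Day 140 value is 0.43 to 0.49, a log shift of −0.71 to −0.84 against the planning SD of 0.312. One such value among 60 pairs moves the log treatment difference by 0.71/60 to 0.84/60, or 0.012 to 0.014: a little over 1% of the ratio, in a direction set by the arm concerned.

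**4. What happens if it is dropped.** With a fixed effect per pair, the treatment contrast uses only pairs with both members present. As a check, 20 simulated pairs with three participants deleted, each from a different pair, gave the same estimate (−0.0076), standard error (0.300) and residual degrees of freedom (16) with and without the three unmatched partners. One lost AUC thus costs one pair, 1/60 = 1.7% of the pairs for that parameter. At GMR 1.08 and no within-pair correlation, power is 81.3% with 60 pairs and 80.7% with 59, about 0.6 points per lost pair.

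**5. What cannot be computed.** The number of participants who would take a prohibited medicine is not in the documents. Steps 3 and 4 give a cost per case, not a cost of the rule.

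**The case against.** The trigger is narrower than the ban first suggests. Section 6.5.1 permits paracetamol, oral contraceptives, postmenopausal hormones, supplements, and short courses of nonprescription drugs that the Investigator judges free of interaction potential. Treatment of a new post-dose illness will mostly fall under the exemption for treatment-emergent events. The volunteers are healthy, and 7.2 says should, with the Medical Monitor contacted beforehand where possible. All of this stands, and it limits how often the rule will bite.

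Follow-up does not stop at once, given the Early Withdrawal Visit, the encouraged later visit and the SAE window. A reader might infer that the rule ends safety follow-up; the documents support only that it is shortened.

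A reader might also infer that each case breaks a pair. It need not. On the profile assumed in the working, the peak comes 6 to 12 days after dosing, so Cmax is usually kept. A replacement may restore the pair, and sensitivity analysis 6 brings back excluded values. But a replacement is discretionary and means dosing another volunteer. One withdrawal sample does not rebuild a profile, and neither judgment nor a sensitivity analysis can recover samples never drawn.

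The most tempting stronger reading concerns power. At 10% loss, 60 × 0.9² = 48.6 complete pairs would be expected without replacement, and power at GMR 1.08 with no pair correlation falls from 77.5% with 54 pairs to 73.0% with 48. Those figures describe dropout and non-evaluability from every cause, and they depend on the correlation: at an assumed 0.2, 48 pairs give 81.1%. They cannot be charged to this rule.

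Finally, a medicine that counts as an important deviation affecting PK would remove the participant from the PKS under SAP 4.4 anyway. That stands for those cases. For the others, continued sampling keeps both options open, whereas withdrawal closes one.

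**Conclusion.** The point holds as a cheap improvement to data collection. Sections 7.1 and 7.2 do not contradict each other, since one concerns the drug and the other the study. Read together, however, they leave item 3 with no effect after Day 1 except to shorten observation. An early case loses more than half of the profile behind AUC and AUC(0-t) at Day 28 and more than a quarter at Day 56; a case at Day 112 loses little. Where a parameter is missing, the partner is lost to that contrast too, unless a replacement is enrolled. These sizes rest on the 28-day half-life, mono-exponential decline and an assumed absorption rate. No bias in a stated direction and no loss of power can be attributed to the rule, because its frequency is unknown.

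**What to change.** Reconcile Protocol 7.2 with the single-dose design, so that use of a prohibited medicine is recorded as a protocol deviation and does not by itself end data collection. State that the already scheduled PK, antibody and safety visits continue to Day 140 with the participant's consent. In the SAP, replace case-by-case judgment on these profiles with criteria for PKS and parameter inclusion, set before concentrations are released. The means exist: Protocol 9.6 and SAP 5.1.1.4 review deviations before database lock, and Protocol 6.3 withholds concentrations from the study team until the last participant's last procedure.

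The prohibited-medication list is unchanged. Care decisions, and any withdrawal for safety, stay with the Investigator.

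The cost is wording in both documents and the conduct of visits already in the schedule. The downside is small: some retained profiles may still be excluded from the PKS under SAP 4.4, so a few samples will be drawn that the primary analysis does not use.
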